### **8.3. Closure Procedure**

Just prior to access site closure, document ACT and systolic BP (ACT should be <250 seconds prior to closure, Systolic BP should be <180mmHg per MANTA VCD IFU but these targets are not mandatory per protocol; capturing ACT and SBP prior to closure is mandatory).

The operator should refer to the study specific U/S-Guided Closure Procedure Instructions located in the site binder for details pertaining to the specific steps for closing the femoral access site using the MANTA VCD. The closure procedure must be performed by an authorized operator.

#### **8.3.1. Time to Hemostasis Measurement**

Time to Hemostasis is the elapsed time between MANTA deployment (withdrawal of sheath from artery) first observed and confirmed arterial hemostasis (no or minimal subcutaneous oozing and the absence of expanding or developing hematoma).

As Time to Hemostasis is an important secondary endpoint for this study, it is critical to measure and document it accurately.

- Time to Hemostasis should be inclusive of any time that manual or mechanical pressure is applied specifically to stop arterial bleeding. Do not include time spent when light digital or mechanical pressure is done to treat oozing, or if short manual compression is done as a preventative measure as part of standard of care.
- If manual or mechanical compression is required, every attempt should be made to check for hemostasis as frequently as logically and medically possible to obtain accurate Time to Hemostasis. It is important to declare hemostasis within 1 minute after it is achieved.

#### **8.3.2. Additional Procedure and Post-closure Required Documentation**

The following items are to be recorded on the eCRF:

- Use of certain medications:
  - Cardiovascular medications (e.g., anti-hypertensives, anti-arrhythmic, etc.), anti-coagulants, anti-thrombotic and anti-platelets
- Use of any adjunctive devices or methods (e.g., lidocaine/epinephrine or thrombin injection beyond institution's standard of care protocol) to obtain hemostasis
- Target Femoral angiogram
- Assessment of adverse events

### **8.4. Post Procedure**

The following assessments will take place post procedure (within 3-12 hours of closure):

- Medication changes
- Target Femoral access site assessment
- Recording of any adverse events

- Ambulation: The following guidelines are provided for ambulation following the MANTA deployment procedure; however, specific ambulation regimes should follow standard hospital procedures and or clinician practices.
  - It is recommended that 6 hours after removal of the MANTA sheath, if the femoral access site is suitable for ambulation and if medically indicated, the subject should be asked to stand at bedside.
  - If the patient successfully stands with no or minimal oozing, the patient should be asked to walk 6 meters (20 feet). If the patient ambulates successfully, record the ambulation time on the CRF.
  - If the patient is unable to walk 6 meters (20 feet), the patient should be returned to bed. Attempt to ambulate the patient at the earliest possible time when the risk of bleeding is minimal. When the patient ambulates successfully, record the ambulation time on the eCRF.

### 8.5. Discharge

The subject is ready for discharge when the subject has ability to walk 6 meters (20 feet), is free from orthostatic hypotension [defined as stable blood pressure and heart rate after ambulating], has the ability to void, and has a stable groin site without bleeding or expansion of a prior hematoma. However, discharge should follow standard hospital procedures and or clinician practices.

The following assessments will take place just prior to discharge:

- Documentation of any changes to medications
- Target Femoral access site assessment
- Recording of any adverse events
- Any subsequent secondary interventions since post procedure (For example, any additional surgical or percutaneous interventions post the index large bore procedure that occurred on the femoral artery of the MANTA (ipsilateral) leg, such as percutaneous coronary intervention (PCI), through the 12 month follow-up phone call.)

The date and time of discharge for each subject should be recorded in the eCRF.

## 9. Study Follow up Visits

### 9.1. 30 Day Office Visit

The following evaluations will be performed in the office/clinic at 30 days ( $\pm$  7 days) post procedure:

- Assess any changes to medications
- Adverse events
- Target Femoral access site assessment
- Any subsequent secondary interventions since discharge (For example, any new surgical or percutaneous interventions post the index large bore procedure that occurred on the femoral artery of the MANTA (ipsilateral) leg, such as percutaneous coronary intervention (PCI), through the 12 month follow-up phone call.)

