## Schedule of Assessments

Table 1: Schedule of Assessments

Assessment	Screening Visit	TAVR Procedure	Closure Procedure			Post-procedure	Discharge	Follow-up (FUP)	
			Pre-closure	Closure	Post-closure			30-day office visit (±7 Days)	12-month Phone (±30 Days)
Subject Eligibility / Informed Consent / Applicable PHI Authorization form*	X								
Medical History	X								
Medications 	X	X	X	X	X	X	X	X	X
Laboratory Tests	X 								
Pregnancy Test	X 								
CT Angiographic Scan	X 								
Ultrasound  (access and assessment)		X		X					
ACT / SBP			X 						
Adjunctive Devices				X	X				
Target Femoral angiography					X 				
Target Femoral access site assessment					X	X	X	X	X 
Time to Hemostasis					X 				
Delayed Ambulation/Discharge						X	X		
Adverse Events			X	X	X	X	X	X	X 
Subsequent Secondary Intervention 							X	X	X

\*Or other form required by applicable U.S. or Canadian laws governing the use and disclosure of individually identifiable protected health information (PHI)

1. The following medications will be recorded on the eCRF for each subject: cardiovascular medications (e.g., anti-hypertensives, anti-arrhythmic, etc.), anti-coagulants, anti-thrombotic and anti-platelets. Any changes to these medications should be documented throughout the course of the 12 month follow up.
2. Considered standard of care and are to be done according to the site's standard of care practice for pre-procedure labs for the TAVR procedure (hemoglobin, creatinine, and platelet count, International Normalized Ratio (INR))
3. Screening Visit CT Scan to assess both limbs for presence/absence/severity of calcium, atherosclerotic disease, tortuosity, and acceptable flow rates
4. Ultrasound for access SOC; Ultrasound data collection during closure
5. Prior to all closure methods, record ACT and systolic BP (per MANTA VCD warnings SBP<180mmHg; recommend ACT<250 seconds prior to closure but these targets are not mandatory per protocol; capturing ACT and SBP prior to closure is mandatory)
6. Post-closure, perform target (ipsilateral) femoral angiography from contralateral access site to ensure patency into the ipsilateral common femoral artery
7. At 12m follow-up, target femoral access site assessment will be questions completed via phone; adverse events will only pertain to target access site

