### **15. Statistical Analysis**

#### **15.1. Study Hypothesis**

##### **15.1.1. Safety**

The primary safety analysis will be performed on the first 75 chronologically enrolled PAC (non roll-in) subjects where an attempt to use the MANTA VCD is made (enrolled subjects without an attempt will not be included). In addition, all Adverse Events recorded during the study will be summarized, and severity and relatedness to the device and/or procedure will be reported. Roll-in subjects will be analyzed separately from the PAC. The primary safety endpoint is any Large Bore Access-site Related VARC-2 Major Vascular complication (LBAR VARC-2 Major) within 30 days as defined in Section 6 and adjudicated by the CEC.

The primary safety hypothesis is that the LBAR VARC-2 Major complication rate (proportion of subjects with one or more) is less than the Performance Goal of 14.2%, as follows:

$$H_0: \pi \geq 0.142$$

vs.

$$H_A: \pi < 0.142,$$

where  $\pi$  is the population LBAR VARC-2 Major complication rate within 30 days.

The primary safety hypothesis is that the rate of LBAR VARC-2 Major complications within 30 days of the procedure is less than the performance goal of 14.2%. Derivation of the performance goal is described below.

Stated in words, the hypothesis is:

Null hypothesis: The rate of LBAR VARC-2 Major complications within 30 days after the procedure is not less than the performance goal of 14.2%

Alternate hypothesis: The rate of LBAR VARC-2 Major complications within 30 days after the procedure is less than the performance goal of 14.2%

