#### **15.3.5. *Timing of Reports***

IDE annual progress reports will be submitted as required per applicable law and regulations. A primary analysis report will be submitted to FDA to support a PMA supplement for revised labeling when the first 75 PAC subjects have completed their 30 day follow-up visit. A final clinical study report will be submitted once all 150 PAC subjects have been enrolled, completed all follow-up visits and have exited the study.

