#### **15.5. *Missing Data***

Every effort will be undertaken to limit premature discontinuations and ascertain completeness of data collection throughout the course of the study. It is unlikely that there would be missing data for the LBAR VARC-2 Major complication endpoint as a 30 day follow-up visit is typically standard of care for TAVR patients; therefore all subjects with an attempted procedure are expected to be followed for at least 30 days. The 12 month follow up assessment will be conducted via phone; sites will ensure that subject contact details are on file correctly when concluding the 30 day visit.

Missing data will not be imputed, and all available data will be summarized.

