6.2 Timing of Reports

In addition to the required IDE annual progress reports, there will be two reports prepared: the primary analysis report once 75 subjects have completed their 30 day follow-up (see details below), and a Final Report.

The primary analysis report will be prepared once the first 75 consecutively enrolled subjects in the PAC have either completed their 30 day visit or withdrawn from the trial. The primary safety endpoint will include subjects from the 75 subjects only unless more than 15 subjects have been enrolled at a single site. If this unlikely situation occurs, then the first 15 enrolled subjects from that site will be included to achieve no more than 20% of patients coming from a single site. All remaining endpoints will summarize what data are available at that time as endpoints are intended to be descriptive in nature and involve no hypothesis testing.

A final report will be prepared once the trial is complete, where all subjects have completed their 12 month visit or withdrawn from the study and sites are closed. All available subject data will be included at this time. A 95% confidence interval for the main safety endpoint will still be prepared but the basis for approval is intended to use the primary analysis report.

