6.3 Primary Safety Endpoint: LBAR Major complications

Endpoint: Large Bore Access-site Related VARC-2 Major Vascular (LBAR Major) Complication within 30 days (adapted from VARC-2 Definitions)¹⁰

- Access site or access-related vascular injury (dissection, stenosis, perforation, rupture, arterio-venous fistula, pseudoaneurysm, hematoma, irreversible nerve injury, compartment syndrome, percutaneous closure device failure) leading to death, life threatening or major bleeding, visceral ischemia, or neurological impairment OR
- Distal embolization (noncerebral) from a vascular source requiring surgery or resulting in amputation or irreversible end-organ damage OR

- The use of unplanned endovascular or surgical intervention associated with death, major bleeding, visceral ischemia or neurological impairment OR
- Any new ipsilateral lower extremity ischemia documented by patient symptoms, physical exam, and/or decreased or absent blood flow on lower extremity angiogram OR
- Surgery for access site-related nerve injury OR
- Permanent access site-related nerve injury

AEs will be reviewed by the CEC to determine if they meet one or more of these criteria and this adjudication for endpoint classification will be used in analysis.

Hypothesis:

The primary safety hypothesis is that the LBAR Major complication rate (proportion of subjects with one or more) is less than the Performance Goal of 14.2%, as follows:

$$H_0: \pi \geq 0.142$$

vs.

$$H_A: \pi < 0.142,$$

where π is the population LBAR Major Complication rate within 30 days.

The primary safety hypothesis is that the rate of LBAR Major complications within 30 days of the procedure is less than the performance goal of 14.2%.

Stated in words, the hypothesis is:

Null hypothesis: The rate of LBAR Major complications within 30 days of the procedure not less than the performance goal of 14.2%

Alternate hypothesis: The rate of LBAR Major complications within 30 days of the procedure is less than the performance goal of 14.2%

Subjects to include:

The first 75 chronologically enrolled subjects in the Analysis Cohort where an attempt to use the MANTA device is made (enrolled subjects without an attempt will not be included).

Statistical Analysis:

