The proportion of subjects with a LBAR Major Complication at 30 days post procedure will be summarized as number, percent and exact 95% 2-sided confidence interval for the calculated proportion. The probability of experiencing at least one LBAR Major complication in 30 days post procedure will be tested versus the performance goal using an exact binomial test comparing to a one-sided alpha of 0.025.

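### After a permitted Day 23 visit, no scheduled inquiry before the primary report covers the rest of the 30-day endpoint window, yet the subject counts as a 30-day non-event

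*Protocol*

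**What the plan says.** **Endpoint window.** The primary endpoint is any LBAR VARC-2 Major complication within 30 days of the procedure (Protocol 6.1 and 15.1.1; SAP 6.3).

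**Visit window.** The Schedule of Assessments lists "30-day office visit (±7 Days"). Protocol 9.1 gives the same tolerance: "The following evaluations will be performed in the office/clinic at 30 days", plus or minus 7 days. The earliest compliant visit is Day 23.

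**Trigger for the primary report.** Protocol 15.3.5 submits it "when the first 75 PAC subjects have completed their 30 day follow-up visit". SAP 6.2 prepares it once those subjects "have either completed their 30 day visit or withdrawn from the trial". Neither requires Day 30 to have passed or status at Day 30 to be known.

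**Who is counted, and how.** SAP 6.3 includes "The first 75 chronologically enrolled subjects in the Analysis Cohort where an attempt to use the MANTA device is made". The estimator is a crude proportion: "The proportion of subjects with a LBAR Major Complication at 30 days post procedure will be summarized as number, percent". Missing data are not imputed (Protocol 15.5; SAP 8), and no minimum follow-up or last-contact rule is given.

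**Follow-up assumption.** Protocol 15.5 reasons that a 30-day visit is usual care for these patients, "therefore all subjects with an attempted procedure are expected to be followed for at least 30 days". SAP 8 repeats this.

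**Next scheduled contact.** This is the 12-month call (Protocol 9.2). Its adverse-event item refers to the period from 30 days to 12 months. Its question on secondary interventions reaches back to the 30-day visit. The primary report does not wait for this call.

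**The concern.** The endpoint and the visit that ascertains it do not end on the same day. A subject seen on Day 23 without an event has had no scheduled question about Days 24 to 30 when the primary report is written. Because the estimator is a crude proportion with no follow-up requirement, that subject is counted exactly like one whose status was checked on Day 30 or later.

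The error has one direction. A missed event lowers the observed rate and favours meeting the performance goal. The report that rests on this rate is the one intended to support the PMA supplement, and its decision boundary is one event wide.

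**Working it through.** **Inputs.** Performance goal 14.2%, assumed rate 4.2%, one-sided alpha 0.025, N = 69 with 75 analysed (Protocol 15.1.1 and 15.2); exact binomial test (SAP 6.3); visit window 30 ± 7 days (Protocol 9.1).

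**1. The plan's own figure.** The rule passes with c or fewer events when P(X ≤ c | n, 0.142) ≤ 0.025, which is equivalent to an exact upper 97.5% bound below 14.2%. The smallest n with at least 80% power at 4.2% is 69, with c = 4, type I error 0.0248 and power 83.6%. The stated 69 is reproduced.

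**2. The boundary at 75.** Here c is still 4.

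| Events | Exact upper 97.5% bound | Result |
|---|---|---|
| 4/75 | 13.1% | pass |
| 5/75 | 14.9% | fail |

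P(X ≤ 4 | 75, 0.142) = 0.0134, so with complete ascertainment the test has slack below 0.025.

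**3. Length of the gap.** 30 − 7 = Day 23, so up to 7 days (24 to 30) follow the earliest compliant visit.

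**4. How often a late event would follow the visit.** Assume visits are spread evenly over the 15 days from Day 23 to Day 37.
- Visits before Day 30: 7/15 = 47%.
- For an event on day e in 24 to 30, the chance that the visit came earlier is (e − 23)/15. Averaged over the seven days this is 4/15 = 27%.

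**5. Expected loss.** Expected major events are 75 × 0.042 = 3.15. The documents give no distribution of event timing, so assume that 0 to 10% of events fall in Days 24 to 30. With no passive capture at all, the share missed is at most 0.10 × 4/15 = 2.7%, and 3.15 × 0.027 = 0.08 events. The range is 0 to about 0.1.

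**6. Effect on type I error at N = 75.** Replace 0.142 by 0.142 × (1 − m), where m is the share of all major events missed.

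| Share missed (m) | P(pass) at a true rate of 14.2% |
|---|---|
| 0 | 0.0134 |
| 2.7% (upper case in step 5) | 0.0167 |
| 5% | 0.0201 |
| about 7.8% | 0.025 |
| 10% | 0.0297 |
| 7/30 (constant hazard, every visit on Day 23, no passive capture) | 0.0784 |

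The last row is an extreme illustration, not an expectation. All rows assume that the 75 stay in the denominator. At n = 69 type I error is 0.0248 before any undercount, so the slack comes from the extra subjects.

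**The case against.** The strongest reply is that follow-up does not stop at the visit. Enrolled subjects are followed until study conclusion (Protocol 7.6). Serious events from attempted placement onwards must reach the sponsor within 24 hours of the investigator's knowledge (11.6). Subjects may volunteer events at any time (11.3). Source documents are reviewed for events the investigators did not report (16.5). Most components of the endpoint, such as death, major bleeding, surgery and amputation, would usually be serious events and are the least likely to escape. This stands. A reader might infer that Days 24 to 30 are unobserved after an early visit; the documents do not support that. What is absent is a scheduled inquiry. Passive routes depend on the event reaching the investigator or the site's records, and milder components, such as new limb ischemia documented by symptoms, are less protected.

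A reader might also infer that the missing-data section contradicts the visit schedule. It does not: it states an expectation, and a Day 23 visit within 12-month follow-up is compatible with it. The window simply does not guarantee it.

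The trigger problem is also narrow in calendar terms. Planned enrollment is 150 over about 12 months, or 150/52 = 2.9 per week. If accrual is even, only about the last 3 of the 75 could be short of Day 30 when the last visit is completed. The 47% above counts early visits, not subjects short of Day 30 at analysis. This limits the timing issue, but the other early-visit subjects still have no scheduled inquiry after their visit.

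The date limit in the 12-month adverse-event item may attach only to part of the sentence, so that call might pick up Days 24 to 30. That would help the final report, not the primary one. The sponsor's CE-mark study also used 30 ± 7 days (Protocol 3.2), but windows for the other ten studies in Table 4 are not shown, so comparability is only partly supported.

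**Conclusion.** The point holds as a gap in ascertainment. The plan lets a visit on Day 23 complete a subject for a 30-day endpoint, and nothing scheduled before the primary report covers the remaining days. The direction is anti-conservative and one event separates pass from fail.

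The likely size is small. Losing at most about 0.1 expected events, with type I error moving from 0.0134 to no more than 0.0167, rests on three assumptions: at most 10% of major events fall in Days 24 to 30, visits are spread evenly over the window, and all 75 subjects are in the denominator. It also ignores passive capture, which would make the loss smaller. Type I error would exceed 0.025 only if about 7.8% of all major events were missed. A reader might take the one-event margin as evidence that the primary conclusion is at risk. The margin shows that a missed event could matter, not that one is likely, and the documents hold no timing data that would make it so. This is a cheap improvement, not a flaw that invalidates the design.

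**What to change.** - **Define completion.** State in Protocol 9.1 and SAP 6.3 that a subject has completed the primary endpoint when access-site event status through Day 30 is confirmed. For visits before Day 30, confirm by chart check or short call on or after Day 30. Alternatively, set the visit window to Day 30 to Day 37.
- **Move the trigger.** In Protocol 15.3.5 and SAP 6.2, tie the primary report to that confirmation instead of to visit completion. SAP 6.2 should also say how subjects who withdraw before Day 30 without an event are counted.

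N, the exact test and the 4-event threshold at 75 are unchanged. The cost is window or eCRF wording, a brief contact or record check for early-visit subjects, and possibly a few days' delay to data lock.

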## 9.2. 12-month Phone Assessments

The following assessments will be collected via phone at 12 months ( $\pm$  30 days) post procedure:

- Assess any changes to medications
- Adverse event inquiry (specific to adverse events related to the MANTA leg and/or a MANTA related adverse event between 30 days and 12 months)
- Target Femoral access site assessment question
- Any subsequent secondary interventions since the 30-day visit (For example, any new surgical or percutaneous interventions post the index large bore procedure that occurred on the femoral artery of the MANTA (ipsilateral) leg, such as percutaneous coronary intervention (PCI), through the 12 month follow-up phone call.)

# 10. Data Management

## 10.1. Electronic Case Report Form (eCRF) Entry

Data from study site medical records and source worksheets will be entered into an online electronic data capture (EDC) system. Qualified study staff at each site will perform primary data collection drawn from source document (hospital chart) review. Sponsor designated monitors will perform clinical monitoring, including review of eCRFs with verification to the source documentation.

Data entry should occur in a timely manner for accuracy, but additionally for complying with regulations if unanticipated or serious adverse event occurs.

## 10.2. Data Management

The Sponsor or its designee will review the data against the original source documents and ensure any noted discrepancies are resolved by the investigational site, in accordance with the separate data management and monitoring plan(s). Subject data will be compared to information originally recorded on source documents related to the trial (e.g., professional notes, laboratory reports, investigation-specific worksheets, etc.). The extent of source document verification may be risk-based.

All information collected in the eCRFs will be entered directly into a secure database. The database design and installation will be validated prior to use.

The details of data review, database cleaning and data querying are described in a Data Management Plan (DMP). This plan may be updated throughout the investigation as amended data management requirements and investigation-specific data conventions are determined.

Data entered by investigational sites will be reviewed on an ongoing basis to ensure adequate query resolution and identify and query adverse events, protocol deviations, and any other ambiguous data points.

